### Concomitant Medications

Medications intake during the study will be recorded and presented in a listing. The medication name, dose, units, route, indication or reason taken, code, date and time taken will be presented. The listing will include the WHO DDE coded terms (e.g., ATC and preferred terms).

## Extent of Exposure

Study product use will be presented in separate listings for each study part and for part B, for each session.

Date, start and end time as well as duration of time a product is used (time spent per cigarette and duration of gum in mouth) will be presented for all entries.

For part A, number of products dispensed and returned will be presented.

For part B uncontrolled usual brand or VLN cigarettes, number dispensed and returned, start and stop times for inhalation, and duration of inhalation will be presented. For part B controlled usual brand or VLN cigarettes, start and stop time for inhalation, inhalation duration, and missed inhalations (and reason for miss) will be presented. For Part B nicotine polacrilex gum, only date, start and end timewill be presented.

Duration of time a product is used, number of inhalations (puffs), and duration of inhalation (per puff) per cigarette for own-brand and VLN cigarettes will also be summarized.

## Clinical Laboratory Evaluations

Planned laboratory analyses include:

Clinical Laboratory Test	Parameters/Details
General biochemistry:	Sodium, potassium, glucose (random), creatinine, total protein, blood urea nitrogen (BUN), albumin, total bilirubin, alanine transferase, aspartate transferase, lactic dehydrogenase, gamma glutamyl transferase, alkaline phosphatase, creatine phosphokinase, FSH a
Hematology:	Hematocrit, hemoglobin, red blood cell count, total and differential (absolute) white blood cell count, platelets
Serology (screening visit only):	Hepatitis B surface antigen (HbsAg), anti-hepatitis C antibodies (HCVAb), human immunodeficiency virus (HIV)
Urinalysis:	Color, pH, snpecific gravity, ketones, protein, glucose, bilirubin, nitrite, urobilinogen, occult blood, microscopic examination of sediment, only if urinalysis dipstick results are abnormal
Urine drug screen:	Tetrahydrocannabinol (THC), opioids (morphine, codeine, heroin, hydrocodone, hydromorphone, and oxycodone), amphetamines, cocaine, and benzodiazepines.

a Postmenopausal women at Screening only.

Separate listings of all individual data for general biochemistry, hematology, urinalysis, serology and urine drug screen will be presented. Abnormal findings will be flagged in the listings.

Biochemistry, hematology and urinalysis results will be summarized by laboratory test and visit.

Subject listings of abnormal on-study laboratory values will be provided. Similarly, clinically significant on-study laboratory data will be presented in a second listing.

## Vital Signs

Vital signs measurements consist of blood pressure, pulse rate, body temperature, and respiratory rate and will be presented in listings.

Descriptive summaries of vital signs will be presented by vital sign test and visit.

Subject listing of abnormal on-study vital signs values (Out-of-Range – NCS or CS) will be provided. Similarly, CS on-study vital signs values (Out-of-Range – CS) will be presented in a second listing.

### Physical Examination Findings

The complete physical examination includes a review of the following: general appearance, head, eyes, ears, nose, throat (HEENT), neck, cardiovascular, respiratory, gastrointestinal, neurological, musculoskeletal/extremities, and skin. The brief physical examination includes a review of general appearance, respiratory, cardiovascular, and gastrointestinal systems. Results of complete and brief physical examinations will be presented in a listing.

Subject listing of abnormal on-study physical examination assessments (Abnormal – not clinically significant [NCS] or clinically significant [CS]) will be provided. Similarly, clinically significant on-study physical examination assessments (Abnormal – CS) will be presented in a second listing.

### Electrocardiogram

Electrocardiograms (ECGs) parameters (heart rate, PR interval, QRS duration, QT interval and QTcF interval) as well as overall assessments (Normal, Abnormal– NCS or Abnormal – CS) will be listed.

ECGs parameters will also be summarized by parameter and visit.

Subject listing of abnormal on-study ECG overall assessment (Abnormal – NCS or CS) will be provided. Similarly, CS on-study ECG overall assessment values (Abnormal – CS) will be presented in a second listing.

## 11. INTERIM ANALYSES AND DATA SAFETY MONITORING

---

There is no interim analysis or safety data monitoring planned for this study.

## 12. CHANGES TO PROTOCOL-SPECIFIED ANALYSES

---

There are no changes to protocol or to specified analyses for this study.

## 13. GENERAL INFORMATION RELATED TO DATA PRESENTATIONS

---

All programs used to generate statistical analyses will be validated according to Algorithme Pharma's standard operating procedures.

TFLs will be displayed on letter size paper, 8 1/2 inches by 11 inches, using the Courier New font.

In general, summary statistics for raw variables (i.e., variables measured at the study site or central laboratory) will be displayed as follows: minima and maxima will be displayed to the same number of decimal places as the raw data. Means, medians, and quartiles will be displayed to one additional decimal place and standard deviations will be displayed to two additional decimal places.

Percentages will be displayed to one decimal place. Percentages between 0 and 0.1 (exclusive) will be displayed as '<0.1'. P-values will be displayed to 3 decimal places. P-values that are less than 0.001 will be displayed as '<0.001'.

The numbers of decimal places for summary statistics of derived variables (i.e., variables that are not measured by the study site but are calculated for analysis based on other measured variables) will be determined on a case by case basis. In general, minima and maxima will be displayed to the commonly used unit of precision for the parameter. Means, medians, quartiles, and confidence limits will be displayed to one additional decimal place and standard deviations will be displayed to two additional decimal places.

The formats and layouts of TFLs are provided in subsequent sections. Actual formats and layouts may be altered slightly from those presented in the templates as necessary to accommodate actual data or statistics. Minor format changes will not require updates to the SAP.

The tables and listings listed below are common data displays. Their numbering and general content follow the ICH E3 guidelines.

## PLANNED FIGURES

### Pharmacokinetic Data

Section 14.2.1	Summary of Plasma Concentration and PK Parameters
Section 14.2.1.1	Summary of Concentration Data
Figure 14.2.1.1.1	Mean ( $\pm$ SD) Unadjusted Plasma Nicotine Concentration Following Administration of Product A, B and C – Controlled Use (Linear Scale)
Figure 14.2.1.1.2	Mean ( $\pm$ SD) Unadjusted Plasma Nicotine Concentration Following Administration of Product A, B and C – Controlled Use (Semi-Log Scale)
Figure 14.2.1.1.3	Mean ( $\pm$ SD) Unadjusted Plasma Nicotine Concentration Following Administration of Product A, B and C – Uncontrolled Use (Linear Scale)
Figure 14.2.1.1.4	Mean ( $\pm$ SD) Unadjusted Plasma Nicotine Concentration Following Administration of Product A, B and C – Uncontrolled Use (Semi-Log Scale)
Figure 14.2.1.1.5	Mean ( $\pm$ SD) Baseline-Adjusted Plasma Nicotine Concentration Following Administration of Product A, B and C – Controlled Use (Linear Scale)
Figure 14.2.1.1.6	Mean ( $\pm$ SD) Baseline-Adjusted Plasma Nicotine Concentration Following Administration of Product A, B and C – Controlled Use (Semi-Log Scale)
Figure 14.2.1.1.7	Mean ( $\pm$ SD) Baseline-Adjusted Plasma Nicotine Concentration Following Administration of Product A, B and C – Uncontrolled Use (Linear Scale)
Figure 14.2.1.1.8	Mean ( $\pm$ SD) Baseline-Adjusted Plasma Nicotine Concentration Following Administration of Product A, B and C – Uncontrolled Use (Semi-Log Scale)

### Pharmacodynamic Data

Section 14.2.3.1	Summary of Questionnaires Responses
Figure 14.2.3.1.1	Mean Tobacco/Nicotine Withdrawal Questionnaire Responses Following Administration of Product A, B and C – Controlled Use (Linear Scale)
Figure 14.2.3.1.2	Mean Tobacco/Nicotine Withdrawal Questionnaire Responses Following Administration of Product A, B and C – Uncontrolled Use (Linear Scale)
Figure 14.2.3.1.3	Mean Tobacco/Nicotine Withdrawal Questionnaire Reduction in VAS score Following Administration of Product A, B and C – Controlled Use (Linear Scale)
Figure 14.2.3.1.4	Mean Tobacco/Nicotine Withdrawal Questionnaire Reduction in VAS score Following Administration of Product A, B and C – Uncontrolled Use (Linear Scale)
Figure 14.2.3.1.5	Mean Direct Effects of Product Questionnaire Responses Following Administration of Product A, B and C – Controlled Use (Linear Scale)
Figure 14.2.3.1.6	Mean Direct Effects of Product Questionnaire Responses Following Administration of Product A, B and C – Uncontrolled Use (Linear Scale)

## PLANNED TABLES

### Demographic Data

Table 14.1.1.1	Subject Disposition (All Subjects)
Table 14.1.1.2	Subject Disposition (Randomized Population [Part A])
Table 14.1.1.3	Subject Disposition (Randomized Population [Part B])
Table 14.1.1.4	Subject Disposition Characteristics (Safety Population)
Table 14.1.1.5	Subject Disposition (Pharmacodynamic Population)
Table 14.1.1.6	Subject Disposition (Pharmacokinetic Population)

Table 14.1.1.7	Subject Disposition (Completer Population)
Table 14.1.2.1	Summary of Demographic Characteristics (Randomized Population [Part A])
Table 14.1.2.2	Summary of Demographic Characteristics (Randomized Population [Part B])
Table 14.1.2.3	Summary of Demographic Characteristics (Safety Population)
Table 14.1.2.4	Summary of Demographic Characteristics (Pharmacodynamic Population)
Table 14.1.2.5	Summary of Demographic Characteristics (Pharmacokinetic Population)
Table 14.1.2.6	Summary of Demographic Characteristics (Completer Population)
Table 14.1.3	Summary of Tobacco Use History (Safety Population)
Table 14.1.4.1	Summary of Product Use Part A (Safety Population)
Table 14.1.4.2	Summary of Second Product Use Part B (Safety Population)

## Pharmacokinetic Data

Tables in this section are based on the pharmacokinetic population unless otherwise stated.

Section 14.2.1	Summary of Plasma Concentration and PK Parameters
Section 14.2.1.1	Summary of Concentration Data
Table 14.2.1.1.1	Summary of Unadjusted Plasma Nicotine Concentration Following Administration of Product A – Controlled Use
Table 14.2.1.1.2	Summary of Unadjusted Plasma Nicotine Concentration Following Administration of Product A – Uncontrolled Use
Table 14.2.1.1.3	Summary of Unadjusted Plasma Nicotine Concentration Following Administration of Product B – Controlled Use
Table 14.2.1.1.4	Summary of Unadjusted Plasma Nicotine Concentration Following Administration of Product B – Uncontrolled Use
Table 14.2.1.1.5	Summary of Unadjusted Plasma Nicotine Concentration Following Administration of Product C – Controlled Use
Table 14.2.1.1.6	Summary of Unadjusted Plasma Nicotine Concentration Following Administration of Product C – Uncontrolled Use
Section 14.2.1.2	Summary of Concentration Data
Table 14.2.1.2.1	Summary of Baseline-Adjusted Plasma Nicotine Concentration Following Administration of Product A – Controlled Use
Table 14.2.1.2.2	Summary of Baseline-Adjusted Plasma Nicotine Concentration Following Administration of Product A – Uncontrolled Use
Table 14.2.1.2.3	Summary of Baseline-Adjusted Plasma Nicotine Concentration Following Administration of Product B – Controlled Use
Table 14.2.1.2.4	Summary of Baseline-Adjusted Plasma Nicotine Concentration Following Administration of Product B – Uncontrolled Use
Table 14.2.1.2.5	Summary of Baseline-Adjusted Plasma Nicotine Concentration Following Administration of Product C – Controlled Use
Table 14.2.1.2.6	Summary of Baseline-Adjusted Plasma Nicotine Concentration Following Administration of Product C – Uncontrolled Use
Section 14.2.1.3	Summary of Pharmacokinetic Parameters
Table 14.2.1.3.1	Summary of Baseline-Adjusted Plasma Nicotine Pharmacokinetic Parameter Following Administration of Product A – Controlled Use
Table 14.2.1.3.2	Summary of Baseline-Adjusted Plasma Nicotine Pharmacokinetic Parameter Following Administration of Product A – Uncontrolled Use
Table 14.2.1.3.3	Summary of Baseline-Adjusted Plasma Nicotine Pharmacokinetic Parameter Following Administration of Product B – Controlled Use

Table 14.2.1.3.4	Summary of Baseline-Adjusted Plasma Nicotine Pharmacokinetic Parameter Following Administration of Product B – Uncontrolled Use
Table 14.2.1.3.5	Summary of Baseline-Adjusted Plasma Nicotine Pharmacokinetic Parameter Following Administration of Product C – Controlled Use
Table 14.2.1.3.6	Summary of Baseline-Adjusted Plasma Nicotine Pharmacokinetic Parameter Following Administration of Product C – Uncontrolled Use
Section 14.2.2	Statistical Analysis of Plasma Pharmacokinetic Parameters
Table 14.2.2.1.1	Pharmacokinetic Statistical Analysis – Product A vs Product B (Pharmacokinetic Population)
Table 14.2.2.1.2	Pharmacokinetic Statistical Analysis – Product A vs Product C (Pharmacokinetic Population)
Table 14.2.2.1.3	Pharmacokinetic Statistical Analysis – Product B vs Product C (Pharmacokinetic Population)
Table 14.2.2.2.1	Between-Product Comparisons of $T_{max}$ and $T_{1/2}$ - Non-Parametric Analysis (First Product Use of Part B)
Table 14.2.2.2.2	Between-Product Comparisons of $T_{max}$ and $T_{1/2}$ - Non-Parametric Analysis (Second Product Use of Stage 2)

## Pharmacodynamic Data

Tables in this section are based on the pharmacodynamic population unless otherwise stated.

Section 14.2.3.1	Summary of Questionnaires Responses
Table 14.2.3.1.1	Use The Product Again – Descriptive Statistics (Pharmacodynamic Population)
Table 14.2.3.1.2	Tobacco/Nicotine Withdrawal – Descriptive Statistics (Pharmacodynamic Population)
Table 14.2.3.1.3	Direct Effect of Product Questionnaire – Descriptive Statistics (Pharmacodynamic Population)
Section 14.2.3.2	Summary of Subjective Effect Parameters
Table 14.2.3.2.1	Summary of Subjective Effect Parameters for Tobacco/Nicotine Withdrawal (Pharmacodynamic Population)
Table 14.2.3.2.2	Summary of Subjective Effect Parameters for Direct Effect of Product Questionnaire (Pharmacodynamic Population)
Section 14.2.3.3	Statistical Analysis of Subjective Effect Parameters
Table 14.2.3.3.1.1	Statistical Analysis of Subjective Effect Parameters for Tobacco/Nicotine Withdrawal – Product A vs Product B (Pharmacodynamic Population)
Table 14.2.3.3.1.2	Statistical Analysis of Subjective Effect Parameters for Tobacco/Nicotine Withdrawal – Product A vs Product C (Pharmacodynamic Population)
Table 14.2.3.3.1.3	Statistical Analysis of Subjective Effect Parameters for Tobacco/Nicotine Withdrawal – Product B vs Product C (Pharmacodynamic Population)
Table 14.2.3.3.1.4	Statistical Analysis of Subjective Effect Parameters for Tobacco/Nicotine Withdrawal (Completer Population)
Table 14.2.3.3.2.1	Statistical Analysis of Subjective Effect Parameters for Direct Effect of Product Questionnaire – Product A vs Product B (Pharmacodynamic Population)
Table 14.2.3.3.2.2	Statistical Analysis of Subjective Effect Parameters for Direct Effect of Product Questionnaire – Product A vs Product C (Pharmacodynamic Population)
Table 14.2.3.3.2.3	Statistical Analysis of Subjective Effect Parameters for Direct Effect of Product Questionnaire – Product B vs Product C (Pharmacodynamic Population)
Table 14.2.3.3.2.4	Statistical Analysis of Subjective Effect Parameters for Direct Effect of Product Questionnaire (Completer Population)

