The current study will include a pre-specified period of abstinence prior to each study product administration day (approximately 20 hours in Part A and prior to controlled-use session in Part B, and 6 hours between controlled and uncontrolled-use sessions in Part B) to minimize the impact that residual nicotine concentrations may have on baseline pharmacodynamic, PK and physiological measurements. Consistent with previously published studies, the current study will include an ad libitum product use session, which will allow the subject to use the product as they would in a “real-world” scenario with no limitation on amount of product used, for up to 4 hours. Controlled and uncontrolled product use sessions are also included in order to compare the pharmacodynamic effects and patterns of use under conditions where subjects are instructed on how to use the product (i.e., [maximum 3 ± 2 seconds per puff] at approximately 30 ± 5 -second interpuff intervals) versus how they would use the product in a typical situation.

The current study will use measures of urge to smoke, positive effects, intent to use the product again, and negative effects as proxy measures for the relative reinforcing efficacy of VLN cigarettes, own-brand cigarettes and 4 mg nicotine polacrilex gum. The ability of the VLN cigarettes to satisfy the urge to smoke over the short term will be assessed using the “Urge to Smoke” question in the Tobacco/Nicotine Withdrawal Questionnaire measure and positive effects will be assessed using the “Is the product ‘Pleasant’ right now?” question in the Direct Effects of Product Questionnaire; both will be administered as 100-point VAS. The “Use Product

Again” bipolar VAS has been included at the end of the ad libitum use session in Part A and 90 minutes after product use in Part B to evaluate overall reinforcement effects of the test products. Additional subjective effects will be assessed with “at-the-moment” VAS (Direct Effects of Product Questionnaire, Tobacco/Nicotine Withdrawal Questionnaire) during the Controlled and Uncontrolled Use Sessions to evaluate the magnitude, onset, and offset of product effects and withdrawal symptoms during and after controlled use of the study products.

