### Pharmacodynamic Parameters

The primary endpoints of this study are the Primary Pharmacodynamic Parameters:

$E_{max\_urge(\text{controlled})}$  and  $E_{max\_plst(\text{controlled})}$

Secondary Pharmacodynamic Parameters:

- Ad libitum Product Use (Part A)
  - Use the Product Again VAS score
  - Product use behavior (number of units consumed, time spent per unit, number of inhalations per cigarette, duration of gum in mouth)
- Controlled and Uncontrolled Product Use (Part B)
  - Tobacco/Nicotine Withdrawal Questionnaire
    - $E_{max\_item(\text{controlled})}$  and  $E_{max\_item(\text{uncontrolled})}$
  - Direct Effects of Product Questionnaire
    - $E_{max\_item(\text{controlled})}$  and  $E_{max\_item(\text{uncontrolled})}$
  - Product use behavior (Uncontrolled Use Sessions; number of inhalations, duration of inhalations [per puff], duration of gum in mouth).

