**Randomized Population (Part A):**

All subjects who are randomized into Part A.

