**Pharmacodynamic Population:**

All subjects who use any study product and have pre-use (Tobacco/Nicotine Withdrawal questionnaire) and at least one post-use (for Tobacco/Nicotine Withdrawal and Direct Effects of Product) VAS score for the Controlled Use Session of Part B. This population will be used for statistical analyses of the pharmacodynamic measures.

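### Part A ratings on Use the Product Again are summarised only for subjects who later give Part B controlled-use scores, so anyone leaving before then is excluded from a Part A result

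*SAP*

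**What the plan says.** SAP Section 4 lists "Use the Product Again VAS score" as a secondary pharmacodynamic parameter under Part A; Protocol Section 10.6.2 does the same. Protocol Section 7.2 explains that the scale is "included at the end of the ad libitum use session in Part A and 90 minutes after product use in Part B", so the same instrument produces both Part A and Part B data.

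The analysis text (Protocol Sections 12.4.3.1 and 12.4.3.2; SAP Section 9, Use the Product Again) calls for descriptive statistics by product and names no population. The population comes from the SAP's Planned Tables. There the pharmacodynamic section opens with "Tables in this section are based on the pharmacodynamic population unless otherwise stated", and Table 14.2.3.1.1 is titled "Use The Product Again – Descriptive Statistics (Pharmacodynamic Population"). Its shell in Appendix C has columns for visit, session and time point, with one N per product.

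SAP Section 5 (and Protocol Section 12.3 in the same terms) admits a subject to that population only with a pre-use Withdrawal score and "at least one post-use (for Tobacco/Nicotine Withdrawal and Direct Effects of Product) VAS score for the Controlled Use Session of Part B".

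Two Part A alternatives already exist. The Randomized Population (Part A) is "All subjects who are randomized into Part A". The Safety Population is used for the other Part A endpoint, in the table titled "Summary of Product Use Part A (Safety Population").

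**The concern.** Part A is a separately randomised crossover that is complete before Part B starts. Whether a Part A rating enters the summary should not depend on what the subject does afterwards. Under the current assignment it does, and the condition is set by two questionnaires that are not the endpoint being summarised.

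This could matter because leaving may be related to the rating. Protocol Section 8.3 allows withdrawal for any reason and discontinuation for adverse events. Tolerance of the gum is screened in a 10-minute trial on Day -1, whereas Part A gives four hours of open access. A subject who disliked or tolerated a product poorly could plausibly leave before Day 4, and that subject's low rating would then be missing from the table. Protocol Section 10.5 treats this scale as reflecting the user's overall view of the product, so it contributes to the abuse-liability picture even though it is not tested. Ratings and consumption from the same sessions would also carry different denominators.

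**Working it through.** **Step 1. Which subjects are kept.** The assignments side by side:

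| Data | Collected | Population for display | Membership requires |
|---|---|---|---|
| Use the Product Again, Part A | End of each session, Days 1–3 | Pharmacodynamic (Table 14.2.3.1.1) | Part B controlled-use scores, Day 4 at the earliest |
| Product use, Part A | Same sessions | Safety (Table 14.1.4.1) | Use of a study product after randomisation |
| Use the Product Again, Part B | 90 minutes after use, Days 4–6 | Pharmacodynamic (Table 14.2.3.1.1) | Part B controlled-use scores |

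Applied to individual subjects:
- Rates all three products, then leaves before the first Part B controlled session: excluded from the table.
- Leaves during Part A after rating one or two products: also excluded.
- Gives evaluable scores in the Day 4 controlled session, then leaves: kept, since the definition does not ask for more than one session.

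The mismatch therefore affects the Part A rows only. For the Part B rows the population is suitable.

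**Step 2. The plan's own figure.** The point does not depend on the sample size, but 54 completers is the base for Step 3, so it was checked. Inputs from Protocol Section 12.2: difference 15.85, SD 28.44, two-sided alpha 0.05, power above 80%. Reading the SD as within-condition, the SD of a paired difference is √2 × 28.44 = 40.22. The noncentrality at n = 54 is 15.85 / (40.22 / √54) = 2.90. Power from the noncentral t is 0.811 with n − 1 degrees of freedom and 0.818 with 2(n − 2). The smallest n reaching 80% is 53 or 52 respectively; rounded up to a multiple of the three sequences, either gives 54. The figure reproduces on that reading.

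**Step 3. Illustrative size.** Neither document gives a dropout rate, so both inputs here are assumptions: a fraction d lost before the first Part B controlled session, and a difference D between leavers' and stayers' ratings of a product.

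- Randomised: N = 54 / (1 − d), rounded up
- Excluded: N − 54
- Shift in a product mean: D × (N − 54) / N

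| d | N | Excluded | Shift, D = 10 | D = 20 | D = 30 |
|---|---|---|---|---|---|
| 0% | 54 | 0 | 0 | 0 | 0 |
| 5% | 57 | 3 | 0.5 | 1.1 | 1.6 |
| 10% | 60 | 6 | 1.0 | 2.0 | 3.0 |
| 15% | 64 | 10 | 1.6 | 3.1 | 4.7 |

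For example, at 15%: 54 / 0.85 = 63.5, so 64; excluded 10; 20 × 10 / 64 = 3.1.

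These are upper values if d is read as total dropout, because later Part B leavers stay in. They also assume that every excluded subject rated the product in question. A contrast between two products moves only if leavers differ from stayers by unequal amounts on the two.

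**The case against.** The strongest reply is that little depends on this table. The rating is secondary and purely descriptive, with no model, interval or test, and the primary endpoints are Part B controlled-use measures for which the population is right. The window for loss is short: Day 1 to the first controlled session on Day 4, within one confinement. No SD is given for this scale. Borrowing the urge SD purely for scale, the standard error of a mean at n = 54 is 28.44 / √54 = 3.9 points, so a shift of 1–3 points is less than one standard error. The SAP also follows Protocol Section 12.3, which gives the pharmacodynamic measures to this population. Finally, requiring entry to Part B tends to keep subjects who rated all three products and appear in the Part B rows too. All of this is fair. It limits the importance of the point, but it does not justify making a Part A result conditional on Part B attendance.

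Two stronger readings are tempting, and the documents do not support them.

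A reader might infer that the excluded ratings vanish from the report. SAP Section 6 says that listings generally cover all enrolled subjects and that everything on the case report form will be listed. The planned title of Listing 16.2.6.1.1 names no population. Only its Appendix D shell adds the Pharmacodynamic restriction. That is an inconsistency within the SAP to be resolved, not a decision to suppress data.

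A reader might also infer from the replacement provision that early dropout is expected and the exclusion is bound to occur. Protocol Section 12.2 only permits replacements and states no rate; the number lost before Part B could be zero.

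**Conclusion.** The point holds for the Part A rows of Table 14.2.3.1.1. As written, a subject who rated one or more products on Days 1–3 but has no evaluable Part B controlled session is excluded, while the same subject's Part A product use is tabulated in the Safety Population.

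The consequence is possible selection in a secondary, descriptive summary. No test, error rate or power figure is affected, and bias is a possibility rather than something the documents demonstrate. Under the assumed 5–15% loss before the first controlled session, about 3–10 subjects would be excluded; with an assumed 20-point difference a product mean would move by about 1–3 points. With no loss before that session the tables are identical under either population. The repair is worthwhile because it is cheap and uses data already collected.

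**What to change.** - Split Table 14.2.3.1.1 into a Part A display and a Part B display, each with its own N.
- Summarise Part A in the Safety Population, using all subjects with at least one Part A score. This matches Table 14.1.4.1 and avoids bringing in a third population. Show n for each product, because some subjects may have rated only one or two.
- Keep the Pharmacodynamic Population for the Part B display.
- Remove the Pharmacodynamic Population restriction from the shell of Listing 16.2.6.1.1 so that it agrees with SAP Section 6.
- Record the departure from Protocol Section 12.3 in SAP Section 12, which currently declares no changes.

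The cost is one extra table shell and a documented change; no new data are needed. The downside is that Part A product means may rest on slightly different subjects, which the n per product makes visible.
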